6 STUDY SETTING

Phase 1

Recruitment and data collection will take place at Kawempe Hospital in Kampala, Uganda. These sites are sufficiently busy to recruit the proposed sample size, have the necessary infrastructure to process blood cultures and have significant experience of running research studies within the labour and post-natal ward. Kawempe Hospital is a national referral hospital for high-risk pregnancies and local deliveries. Approximately 25,000 births occur at Kawempe annually, with approximately 11,000 neonatal admissions annually. Mulago Hospital is a large hospital with children's services(43). Electronic health records are currently used in both including antenatal and perinatal information, which are generated by digital data entry from paper hospital records. Blood cultures are currently processed at Makerere Microbiology Laboratories (College of American Pathologists accredited) using BACTEC machines within 12 hours of collection(43).

Phase 2

Data analysis and modelling will take place in collaboration with the Advanced Research Computing Centre at University College London.

Phase 3

Recruitment and data collection will take place at Sally Mugabe Central Hospital in Harare, Zimbabwe. Again, this site is large enough to recruit the proposed sample size, with 22,000 births annually, and has existing research infrastructure to enable quality data collection(41). The Neotree platform is in routine use at Sally Mugabe Central Hospital.

7 SAMPLE AND RECRUITMENT

7.1 Eligibility Criteria

7.1.1 Inclusion criteria

All neonates born at one of the study sites are eligible for recruitment. Where mothers have had an ultrasound scan during pregnancy during routine care, neonates will be eligible for inclusion if they are born at ≥ 34 weeks gestational age. For mothers who have not had an ultrasound scan during pregnancy or have uncertain dates, neonates will be eligible for

Using machine learning to model early-onset neonatal sepsis risk in Uganda (NeoRisk)

inclusion if their birth weight is $\geq 1400\text{g}$ which will include the majority of births ≥ 34 weeks according to the results of the INTERGROWTH-21st Project(44).

7.1.2 Exclusion criteria

Neonates born at <34 weeks gestational age will be excluded due to their higher background risk of sepsis, and automatic admission to the neonatal unit with antibiotic administration. Similarly, neonates with congenital abnormalities or syndromes associated with increased susceptibility to infection will be excluded (e.g. gastroschisis). Neonates whose mothers are unable to provide informed consent will also be excluded. There are no exclusion criteria on the basis of maternal medical or obstetric comorbidities.

7.2 Sampling

7.2.1 Size of sample

Phase 1: There is currently no accepted way to power a machine learning study, the consensus being that more data will always create a better model. However, to ensure the success of this study, we have investigated approximate power to create a diagnostic test to estimate the sample size needed for this study. We have also reviewed this sample size calculation with our collaborators at the UCL Advanced Research Computing centre.

A study of a diagnostic test with 90% sensitivity and a background sepsis rate of 5% (the estimated rate of culture-positive sepsis in Kampala based on previous studies is 12.8%(13) amongst those with clinical signs of sepsis, and up to 5% amongst all neonates according to unpublished data from previous studies at Kawempe) would require 1460 participants (95% confidence interval), as described by Buderer and Jones *et al*(45,46).

This sample size has also been calculated according to three suggested methods for calculating the sample size for a clinical prediction model:

- Calculation of size needing to provide precise estimate of overall outcome risk
- Calculation of size needed to produce predicted values with a small mean error across all individuals
- Size needed considering shrinkage of predictor effects

All of the above methods produced sample sizes from 140-1532, hence the size of 1600 should be sufficient even with some loss to follow up. If, at interim analysis, the rate of culture-positive sepsis is significantly lower, we will explore methods to increase our sample size such as using existing data to create simulated data to train our model.

Phase 3: The sample size will be 900 mothers; this is powered to give 95% confidence for a diagnostic test which has 90% sensitivity with a background rate of clinical sepsis of 16%, using the same calculation method as for the sample size in Phase 1. Although there are limited previous studies of neonatal sepsis prevalence in Zimbabwe using blood cultures, particularly amongst all neonates, one study found a culture-positive sepsis rate of 21% amongst NICU admissions(47), and a recent study reported a clinical diagnosis rate of 40.8%(48) . Therefore, this sample size should give an estimated 367 episodes of clinician-diagnosed sepsis, deemed by Collins *et al.* to be sufficient for external validation of a prognostic model(49).

Using machine learning to model early-onset neonatal sepsis risk in Uganda (NeoRisk)

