The TRIPOD (Transparent reporting of a multivariable prediction model for individual prognosis or diagnosis) statement have been followed in the design of this study and will be followed in its reporting(42). Adjustments will be made as necessary with the release of upcoming artificial intelligence-specific guidelines.

Data analysis

Phase 2 will constitute the main data analysis for data from Uganda.

There will be two main streams to data analysis, which will be completed using R and in collaboration with the Advanced Research Computing Centre at UCL.

1. Machine learning analysis:
 - a. Data from Phase 1 will form a ‘training data set’, with 20% reserved for testing and validation, and be fed into a pre-programmed machine
 - b. Previous methods used for sepsis prediction that will be investigated include gradient tree boosting and neural networks
 - c. Bootstrapping will be considered
 - d. Determination of the exact machine learning model will depend on the data obtained, but the following will be considered:
 - i. Weighted inputs: Allows scaling of measurements
 - ii. Conformal prediction: Allows the machine to determine how uncertain its prediction is, based on distribution of data it has, and missing data
 - iii. Recurrent neural networks: Allows the machine to recognise time-dependent patterns
 - iv. Gradient descent: A method of ‘training’ a machine to minimise the error between prediction and reality by gradually adjusting its weights
2. Traditional logistic regression will be used to identify risk factors associated with clinical and microbiological diagnoses of neonatal sepsis. Although the principal model will be created using machine learning techniques, logistic regression will be

Using machine learning to model early-onset neonatal sepsis risk in Uganda (NeoRisk)

used as a second check of results and to provide additional context with which to interpret the machine learning model

For **Phase 3**, data will be inputted to the machine learning model from Phase 2, and the sensitivity, specificity, positive predictive and negative predictive values calculated, as well as the AUC value.

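### Kampala sensitivity: the only evaluation set the plan commits to is a 20% hold-out with at most about 16 expected cases, while the sensitivity-based sample size rests on 73; resampling on all cases would be a cheap improvement

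*Combined protocol and SAP*

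**What the plan says.** Section 7.2.1 (Size of sample) starts the Phase 1 justification from "A study of a diagnostic test with 90% sensitivity and a background sepsis rate of 5"%, which "would require 1460 participants (95% confidence interval"). The 5% is described as "up to 5% amongst all neonates according to unpublished data from previous studies at Kawempe". Three prediction-model calculations are also cited. All the methods together give 140 to 1532, "hence the size of 1600 should be sufficient even with some loss to follow up".

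For Phase 3 the same section says "The sample size will be 900 mothers", based on "90% sensitivity with a background rate of clinical sepsis of 16"%, "using the same calculation method as for the sample size in Phase 1". It then expects 367 episodes of clinician-diagnosed sepsis. No half-width is printed for either phase.

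Section 4.2 (Outcome) lists sensitivity, specificity and predictive values of the model for participants in both Kampala and Harare. Section 5 (Data analysis, machine learning stream) uses the Phase 1 data for training, "with 20% reserved for testing and validation". It lists bootstrapping only as something to be considered. It does not say on which data the Kampala accuracy measures will be estimated.

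**The concern.** The sample size section and the analysis section assume different numbers of cases. 1460 describes the precision of Kampala sensitivity only if every Phase 1 case contributes to the estimate. The split in Section 5 leaves about a fifth of the cases for evaluation. If sensitivity is read off that fifth, a listed outcome will be reported with far less precision than the sample size section suggests. Section 1 also says that risk assessment in this setting should put sensitivity ahead of specificity, so this is the accuracy measure that the plan itself ranks first.

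The missing half-widths make the gap hard to see. A confidence level alone does not tell the reader how precise a sensitivity estimate from 1460 or 900 infants was meant to be.

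**Working it through.** **Inputs.** Sensitivity 0.90, prevalence 0.05 (Phase 1) and 0.16 (Phase 3), 95% confidence, sizes 1460, 1600 and 900, and 367 expected episodes, all from Section 7.2.1. Hold-out share 0.20, from Section 5.

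**Cases behind each figure.**
- 1460 × 0.05 = 73
- 1600 × 0.05 = 80
- Hold-out: 0.20 × 1600 = 320 infants; 320 × 0.05 = 16

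Since 5% is an upper figure, 80 and 16 are upper expectations.

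**Can 1460 be reproduced?** Not from the printed inputs alone, because the half-width w is missing. It can be solved for:
- Normal approximation, w = 1.96 × √(0.90 × 0.10 / cases). With 73 cases, w = 0.069.
- Wilson interval at 0.90. With 73 cases, w = 0.070, and 73 / 0.05 = 1460 exactly.

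So 1460 fits a target of about ±7 points.

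**Can 900 be reproduced?** 900 × 0.16 = 144 cases, and the normal half-width is 0.049. By Wilson, ±5 points needs 141 cases, and 141 / 0.16 ≈ 881, which 900 covers. So 900 fits a target of about ±5 points. With the 367 episodes expected in the same section, the half-width would be 1.96 × √(0.09 / 367) = 0.031.

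**Precision of Kampala sensitivity, by the data used (exact Clopper-Pearson 95% intervals).**

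| Data | Expected cases | Example result | Exact 95% interval | Width (points) |
|---|---|---|---|---|
| 20% hold-out of 1600 | at most about 16 | 14/16 (87.5%) | 61.7% to 98.4% | 36.8 |
| 20% hold-out of 1600 | at most about 16 | 15/16 (93.8%) | 69.8% to 99.8% | 30.1 |
| Basis of 1460 | 73 | 66/73 (90.4%) | 81.2% to 96.1% | 14.8 |
| All 1600 | at most about 80 | 72/80 (90.0%) | 81.2% to 95.6% | 14.3 |

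Sixteen cases cannot give exactly 90%, so the two nearest results are shown. The hold-out interval is 30.1 / 14.8 = 2.0 to 36.8 / 14.8 = 2.5 times as wide as the one at 73 cases. The exact form is used because the normal half-width at 16 cases (±14.7 points) would put the upper limit at 104.7%.

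**The case against.** Four points can be made for the plan.

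1. **The hold-out may not be the source of the estimate.** Section 5 does not say that Kampala sensitivity will come from the hold-out alone, it leaves bootstrapping open, and Section 3 relies on a second population for external testing. This stands: the imprecision is conditional. But the hold-out is the only Kampala evaluation the plan commits to, and Phase 3 cannot supply a Kampala estimate.

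2. **1460 did not fix the sample size.** The adopted 1600 exceeds the top of the 140 to 1532 range, so a larger calculation was binding. This also stands, and the prediction-model calculations are not challenged here. But 1460 is the only Phase 1 size presented as a sensitivity calculation.

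3. **An untouched test set has value.** It is simple and visibly separate from model building. That is a real advantage, though a costly one with so few cases.

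4. **Different precision by phase is legitimate.** A reader might infer an arithmetic error: with one common half-width the two sizes should differ 0.16 / 0.05 = 3.2-fold, yet they differ 1460 / 900 = 1.62-fold. The documents do not support that reading. Using the same calculation method does not promise the same half-width, and both sizes fit round targets (about 7 and 5 points). Nor can it be said that Phase 1 was planned to be less precise than Phase 3. No target is printed for either phase, and 900 has a second justification, so it may exceed its minimum.

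**Conclusion.** This is a cheap improvement, not a flaw that undermines the study. If Kampala sensitivity is taken from the 20% hold-out, it would rest on at most about 16 expected cases, with an exact 95% interval of roughly 62% to 98%. The 73 cases behind 1460, or the 80 expected in all 1600, would give about 81% to 96%. The figures assume a sensitivity near 90% and the full 5% rate; a lower rate would widen the intervals. The all-case interval is a guide to what resampling could reach, since correcting for optimism adds some uncertainty of its own.

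The unprinted half-widths are a gap in reporting. They do not show that 1460 or 900 is wrong.

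**What to change.** **Main change, Section 5 (Data analysis).** Replace the single 20% hold-out and the tentative reference to bootstrapping with a commitment: Kampala sensitivity and the other accuracy measures will be estimated by resampling-based internal validation on all Phase 1 cases. Bootstrap optimism correction or repeated cross-validation would serve, provided that every modelling and threshold-selection step is repeated within each resample.

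**If the hold-out is kept.** State in Section 7.2.1 that its sensitivity estimate rests on at most about 16 expected cases, with an exact 95% interval of roughly 62% to 98%.

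**Clarification, Section 7.2.1.** Print the half-width used for each phase, taken from the sponsor's own calculation. Before giving one for Phase 3, reconcile the 16% rate (144 cases, about ±4.9 points) with the 367 expected episodes (about ±3.1 points).

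**Cost.** Protocol wording and more computation; no extra participants. There would no longer be a single untouched Kampala test set, although Phase 3 still provides external validation.

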1 BACKGROUND

Sepsis is a leading cause of neonatal mortality worldwide(1), affecting 39.3 per 1000 live births in low- and middle-income countries(2). Mortality from early-onset sepsis can be reduced with prompt, correct treatment with antibiotics(3); therefore, identifying those at risk early is crucial. The sepsis rate in Uganda is high, with an incidence of 68 per 1000 live births, and is highest in hospital facilities(4).

Antibiotics are recommended for neonates with specific risk factors for sepsis, and those with signs of illness, including poor feeding and drowsiness(5). However, many low-resource settings diverge from the World Health Organization (WHO)'s recommended regimens, often due to antimicrobial resistance (5–7) or drug availability(8). Ideally, antibiotics should be given within an hour of birth in cases of suspected early-onset sepsis, which accounts for almost ¾ of sepsis cases in Uganda(4,9).

Additionally, risks of antimicrobial resistance are increasing. Neonates with sepsis in low- and middle-income countries show significant rates of resistance to the extent that the majority of proven infections are resistant to first and second line WHO-recommended antibiotics(10,11). Mortality from sepsis is double with resistant versus sensitive organisms(12). Previous studies in Kampala have shown high rates of resistance to first-line antibiotics(13). Prolonged antibiotic therapy without proven infection is associated with morbidity and mortality in preterm infants, and may affect normal flora and immunity(14,15). Therefore, antimicrobial stewardship is vital for low-resource settings. Accurate, early identification of at-risk neonates allows the benefits of early treatment whilst minimising the harms of overtreatment, and unnecessary admission.

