4.2 Outcome

- Primary outcome for Phase 1: Positive blood culture amongst neonatal participants
- Primary outcome for Phase 3: Clinician (specialist neonatal or paediatric doctor) diagnosis of sepsis amongst neonatal participants as documented in clinical notes or discharge letter
- Clinical features of neonatal sepsis as listed in GAIA neonatal infections case definition
- Admission to neonatal unit
- Readmission to hospital in first 28 days amongst neonatal participants
- Death before 28 days of age
- Sensitivity, specificity, positive and negative predictive value of risk stratification model for participants in Kampala and Harare

Using machine learning to model early-onset neonatal sepsis risk in Uganda (NeoRisk)

5 STUDY DESIGN and METHODS of DATA COLLECTION AND DATA ANALYSIS

There will be three main phases to this study, which is an observational cohort study.

Using machine learning to model early-onset neonatal sepsis risk in Uganda (NeoRisk)

Phase 1 will take place at Kawempe Hospital in Kampala, Uganda. Participants will be recruited from labour wards by study staff, and interim analysis will be completed after recruitment of 10% of the total sample. See section 7.3 for further details.

Data will be collected via an online CRF, including the factors listed in the table in Section 3.

Additionally:

- All neonates within the study will have a **neonatal venous blood sample** taken for culture by designated study staff
 - This must be taken before administration of antibiotics or within 48 hours of birth, whichever is sooner, and regardless of whether the neonate is being investigated and treated for sepsis.
- **Postnatal information** will be collected via telephone at 1 month including maternal and infant outcome, hospital readmission or clinical illness, and vaccines given

All data will be checked for quality control by a member of the study team.

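### Phase 1 is sized at a 5% culture-positive rate that its own source gives as an upper limit; 1600 infants meet the stated requirement only at or very near that rate

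*Combined protocol and SAP*

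**What the plan says.** The Phase 1 primary outcome (Section 4.2) is "Positive blood culture amongst neonatal participants", and every participant is cultured whether or not sepsis is suspected. Section 7.2.1 considers a diagnostic test with 90% sensitivity at a 5% background rate and concludes that this "would require 1460 participants (95% confidence interval"). It cites two rates. One is 12.8%, which applies to neonates with clinical signs. The other is "up to 5% amongst all neonates according to unpublished data from previous studies at Kawempe".

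The section also mentions three sample-size methods for prediction models. It reports an overall range of 140 to 1532 without inputs, and judges 1600 to be enough even after some loss to follow-up.

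Section 7.1.2 states that infants born before 34 "weeks gestational age will be excluded due to their higher background risk of sepsis". It also excludes infants with abnormalities that raise susceptibility to infection.

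A lower rate is foreseen in one clause: "If, at interim analysis, the rate of culture-positive sepsis is significantly lower", the team will look for ways to enlarge the sample. The only example given is simulated data for training. Section 5 places this review at 160 participants.

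**The concern.** A figure described as an upper limit is used as the expected value, and the eligibility rules can only hold the rate steady or push it down. In this type of calculation the required number is inversely proportional to the rate, so any shortfall carries straight through to the number of culture-positive infants. Those infants fix the precision of sensitivity, and they are also the events available for modelling a long list of candidate predictors. The section shows no result at a lower rate, so a reader cannot see how quickly the assurance about 1600 is lost.

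**Working it through.** **Inputs.** From Section 7.2.1: sensitivity 90%, rate 5%, 95% confidence, 1460 required, 1600 planned. From Section 5: pilot of 160. The half-width W is not stated, so it is treated as unknown.

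**The plan's figure.** The cited approach is N = 1.96² × Se(1 − Se) / (W² × rate).

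- Se 90%, W = 5 points (assumed): 0.3457 / 0.0025 = 138.3 cases; 138.3 / 0.05 = 2766. This is not 1460.
- Se 90%, N = 1460: cases = 1460 × 0.05 = 73; W = 1.96 × √(0.09/73) = 6.9 points.
- Se 95%, W = 5 points: 72.99 cases; 72.99 / 0.05 = 1459.8, which matches 1460 but not the stated sensitivity.
- Phase 3, said to use the same method: Se 90%, W = 5 points, rate 16% gives 138.3 / 0.16 = 865, close to the stated 900.

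With the stated 90% sensitivity, 1460 therefore corresponds to an unstated half-width of about 6.9 points.

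**Scaling to lower rates.** Holding 73 cases, N = 73 / rate. At 1600 infants, cases = 1600 × rate and half-width = 1.96 × √(0.09 / cases). Only the 1460 is the plan's number; the rest is scaled from it.

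| Rate | N for 73 cases | Cases in 1600 | Half-width at 1600 (points) |
|---|---|---|---|
| 5% | 1460 | 80 | 6.6 |
| 4% | 1825 | 64 | 7.3 |
| 3% | 2433 | 48 | 8.5 |
| 2% | 3650 | 32 | 10.4 |
| 1% | 7300 | 16 | 14.7 |

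**Headroom in 1600.** Break-even rate with no losses: 73 / 1600 = 4.56%. With an assumed 5% loss: 73 / 1520 = 4.80%. A loss of 1 − 1460/1600 = 8.75% uses all of it at 5%.

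**The pilot.** Expected positives in 160 are 8 at 5% and 4.8 at 3%. The plan gives no threshold. As an illustration, take 3 or fewer positives as the trigger, which occurs with probability 0.039 at a true 5% (binomial). It fires with probability 0.11 at a true 4%, 0.29 at 3%, 0.60 at 2% and 0.92 at 1%.

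**The case against.** Several points on the other side are sound.

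- **A reader might infer that the eligible rate must be below 5%.** The documents do not establish this. The reference to all neonates stands in contrast to those with clinical signs, so it may mean regardless of signs and not all gestations. The source is unpublished, and nothing says whether it included infants under 34 weeks. Section 7.1.1 also admits infants by birth weight of at least 1400 g where dates are uncertain, so some under 34 weeks may enter.
- **A reader might multiply other figures in the protocol to reach a rate well under 1%.** Section 1 describes Uganda "with an incidence of 68 per 1000 live births" and almost three quarters of cases as early-onset; with the 12.8% yield, 0.068 × 0.75 × 0.128 = 0.65%. That product is not a usable estimate. It applies a national incidence to a referral hospital for high-risk pregnancies, and it assigns no positive cultures to infants without suspected sepsis, whereas Phase 1 cultures everyone.
- **A reader might conclude that the pilot cannot detect a low rate.** Under the illustrative trigger it usually would detect 1%. It is weak for moderate shortfalls, around 3% to 4%. The trigger is an illustration, since the plan does not define its criterion as a test.
- **1600 does not rest on 1460 alone.** The three prediction-model methods also support it, but without their inputs nobody can check how they behave at lower rates.
- **The margin may be less committed than the plan implies.** Cultures are taken within 48 hours of birth, so loss at the one-month call need not remove an outcome. Even with no losses, though, the margin ends at about 4.6%.
- **The plan does anticipate a lower rate,** and Section 5 allows the data collection form to be shortened after the pilot. But simulated data add no real culture-positive infants and cannot narrow the interval for sensitivity, and no threshold triggers any action.

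**Conclusion.** The point stands as an untested input assumption. The 5% rate is an upper limit by the plan's own description, the eligible rate may be lower, and 1600 infants deliver the 73 cases behind 1460 only at about 4.6% or above. At 3% the study would have 48 cases and a half-width of 8.5 points; at 2%, 32 cases and 10.4 points. How far the true rate falls below 5% cannot be determined from the documents.

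These figures rest on the inverse-rate formula, on 90% sensitivity, and on every culture-positive infant counting towards the estimate. The last is favourable: Section 5 reserves 20% for testing and validation, and those 320 infants would hold 16 cases at 5%.

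The unstated half-width is a second gap. If 5 points was intended with 90% sensitivity, 1600 falls short of the 2766 needed even at 5%. A reader might infer from the exact match at 95% sensitivity that the wrong value was entered. The documents do not show that; they show only that the precision target must be stated.

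**What to change.** In Section 7.2.1:

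1. Label 5% as an upper limit, and say whether the unpublished figure included infants under 34 weeks.
2. State the half-width, and reconcile it with 90% sensitivity and 1460.
3. Tabulate expected culture-positive cases and the precision of sensitivity at 1600 for rates of 1% to 5%.
4. Limit the statement that 1600 is enough to rates at or near 5%.
5. Replace the undefined pilot criterion with a rule on projected total culture-positive events, using the pilot estimate and its confidence interval against a stated minimum. Name the consequence: fewer candidate predictors and wider stated precision.
6. Do not count simulated data as added sample size.

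The cost is protocol wording and a less favourable stated precision. No extra participants are needed.
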